7.1 Diseases and Therapeutic Area

Secondary hyperparathyroidism (SHPT) is a common complication of chronic kidney disease (CKD) (Goodman, 2004). As kidney function declines this causes disturbances

in the balance of calcium, phosphorous and vitamin D and consequently cause CKD-related mineral and bone disorders (CKD-MBD). These biochemical imbalances of increased calcium, phosphate lead to an overproduction of parathyroid hormone (PTH) and parathyroid gland hyperplasia which characterizes SHPT. Elevated levels of PTH can develop at early stages of CKD even when calcium and phosphorous are within normal range limits (Martinez *et al*, 1997). The impact of SHPT on progressive CKD results in bone mass reduction and an impaired rate of bone remodeling. This inadequate control of SHPT can consequently lead to increased risks of vascular calcification, fractures and cardiovascular morbidity and mortality (Horl, 2004). Approximately 30-47% of severe CKD patients on dialysis in Europe are affected with SHPT (PTH>300 pg/mL) (Hedgeman *et al*, 2015).

Prevention and treatment of SHPT remains a challenge although successful management can be partially achieved with standard treatment with dietary phosphate restriction, phosphate binders, vitamin D and parathyroidectomy. However, the introduction of calcimimetic agents has provided an alternative therapeutic option to manage SHPT. Calcimimetics acts as an allosteric activator by selectively binding to calcium-sensing receptors (CaSR) in the parathyroid gland which lowers the CaSR action of extracellular calcium ions on PTH secretion; and thereby reducing PTH levels and accompanying serum calcium levels (Rodriguez *et al*, 2015).

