8.3 Exploratory

- 8.3.1 To explore the number of HD patients who initiate cinacalcet (i.e. first prescription) with hypocalcemia (*Cohort A*)

HD patients with cinacalcet prescription and serum calcium >8.4 mg/dL at baseline

(Cohort B)

- 8.3.2 To explore the incidence of hypocalcemia events among HD patients with cinacalcet prescription according to PTH levels
- 8.3.3 To explore the frequency of hypocalcemia events among HD patients with cinacalcet prescription according to PTH levels

Hypocalcemia HD patients with cinacalcet prescription (Cohort 1)

- 8.3.4 To explore kinetics of hypocalcemia events in cinacalcet patients with more than one episode of hypocalcemia
- 8.3.5 To explore the impact of hypocalcemia treatment on serum calcium level
- 8.3.6 To explore the impact of hypocalcemia cardiovascular events (CVE) or death

9. Research Methods

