9.3.2 Outcome Assessment

Table 1 summarizes the outcomes to be assessed according to each objective.

Table 1. Outcomes for analysis

Objective	Definition
PRIMARY OBJECTIVES	
Hypocalcemia HD patients with cinacalcet prescription	
- Rate of cinacalcet discontinuation	- Number of patients who discontinue cinacalcet. Discontinuation is defined as the time point beyond which there were ≥ 90 consecutive prescription-free days.
-Cinacalcet prescribing pattern	- No change, dose reduced (relative to dose prior to hypocalcemia), discontinued, Dose increased (relative to dose prior to hypocalcemia)
- Prescribing pattern for any treatment and each of the following drugs: paricalcitol, older AVD, phosphate binder, dialysate calcium and CVD medications	- No change, dose reduced (relative to dose prior to hypocalcemia), discontinued, Dose increased (relative to dose prior to hypocalcemia)
SECONDARY OBJECTIVES	
HD patients with cinacalcet prescription	
- Incidence of hypocalcemia	- First occurrence of a serum calcium (< 8.4 vs. ≥ 8.4 mg/dL) - First occurrence of serum calcium defined by severity: mild (serum calcium ≥ 8.0 - < 8.4 mg/dL), moderate (serum calcium ≥ 7.5 - < 8.0 mg/dL), severe (serum calcium < 7.5 mg/dL)
Hypocalcemia HD patients who discontinued cinacalcet prescription	
- Rate of cinacalcet re-initiation	- Number of patients who re-initiate cinacalcet prescription following discontinuation (yes/no)
- Prescribing pattern for each of the following drugs: cinacalcet, paricalcitol, older AVD, phosphate binder, dialysate calcium and CVD medications	- No change, dose reduced (relative to dose prior to hypocalcemia), discontinued, Dose increased (relative to dose prior to hypocalcemia)
EXPLORATORY OBJECTIVES	
- Incidence of hypocalcemia by PTH	- No. of patients with hypocalcemia according to PTH levels: low (< 10 ng/L or pg/mL), normal (10-65 ng/L or pg/mL) or high (> 65 ng/mL or pg/mL)
- Kinetics of hypocalcemia	- Progressors (subsequent events were more severe than initial events), remitters (subsequent events were less severe than initial events), fluctuators (events ranged in severity with no trend in one direction)
- Changes in calcium level	- Changes in mean or median calcium levels following changes in treatment treatment
- Cardiovascular event	- Any coronary artery event (CVE), cerebrovascular event (CVE), peripheral arterial event (PAE), congestive heart failure event (CHFE), or sudden cardiac event (SCE)

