Laboratory parameters	Hemoglobin [g/dL]	<10, 10-<12, ≥12	baseline
	Ferritin [µg/L]	<500, ≥500	baseline
	CRP [mg/L] *	Quartiles	baseline
	Serum albumin [g/L] *	Quartiles	time-varying
	Creatinine [µmol/L] *	Quartiles	baseline
	Total calcium [mmol/L]	<2.10, 2.10-2.37, >2.37	time-varying
	Phosphate [mmol/L]	<1.13, 1.13-1.78, >1.78	time-varying
	Alkaline phosphatase	<44 IU/mL, 44-147 IU/mL (normal), >147	time-varying

	PTH [pg/mL]	<150, 150-<300, 300-<600, ≥600	time-varying
Medication use	Cinacalcet use [§]	Yes/No	time-varying
	Paricalcitol use [§]	Yes/No	time-varying
	Older AVD use [§]	None; Alfacalcidol; Calcitriol; both	time-varying
	Phosphate binder use [§]	None, Only calcium-based, Only non calcium-based, Any	time-varying
	Cardiovascular medication [§]	Yes/No	time-varying

01 August 2009. If the baseline period or the interval corresponding to the time-varying analysis includes the publication of the KDIGO guidelines, then the value of the value of exposure period pre-KDIGO covariate will be set to Yes; [§] relevant ATC codes in Appendix B; ^{} The quartiles' cut-offs for these variables will be derived at baseline.

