9.6.2 Planned Method of Analysis

9.6.2.1 Descriptive Analysis

Baseline characteristics of patients who do vs. do not develop hypocalcemia until end of follow-up of 12 months will be summarized for patients who initiate cinacalcet using descriptive statistics. Summary statistics will be presented for the time-varying covariates of Table 2 for the 90 days prior to initiation, discontinuation and re-initiation for cinacalcet. Continuous variables will be described using the mean and standard deviation, median, 25th and 75th percentiles and minimum and maximum values. Ordinal or skewed variables will be described using a median and range or categorized into meaningful categories at which point categorical data analysis will be applied. Categorical data will be reported as counts and frequencies.

Summary statistics will also be presented for time to first hypocalcemia event, time to any treatment intervention following hypocalcemia event, and time to cinacalcet re-initiation. In addition, cinacalcet prescribing patterns at initiation, at time of hypocalcemia event and after hypocalcemia event and treatment patterns (e.g. vitamin D, phosphate binders and CVD medications) 90 days prior to cinacalcet initiation, at time of cinacalcet initiation, at time of hypocalcemia event, and time of cinacalcet re-initiation will be described. Number of HD patients who initiate cinacalcet with hypocalcemia (<8.4 ng/mL) amongst all cinacalcet users will also be counted.

Plot median and IQR of PTH, calcium and phosphate values every month or quarter during the 12 months following cinacalcet initiation, following hypocalcemia event and following cinacalcet re-initiation. The resulting data will be arranged graphically, stratified by levels of control (Table 3) during the baseline period, to depict the longitudinal pattern of laboratory values following initiation, discontinuation and re-initiation of treatment.

Smoothing techniques may need to be employed to fit the patterns of the laboratory data trajectory.

Table 3. Levels of control

	Serum PTH (pg/mL)	Serum Calcium (mmol/L)	Serum Phosphate (mmol/L)
Low	<150	<2.10	<1.13
Medium	Medium low 150<300	2.10-<2.37	1.13-<1.78
	Medium high 300-<600		
High	≥600	≥2.37	≥1.78

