9.6.2.4 Exploratory objective endpoints

Point estimates and 95% confidence intervals will be derived to determine the rate of hypocalcemia according to PTH levels during the 12 months following cinacalcet initiation.

To explore the kinetics of hypocalcemia, we will plot serum calcium level after first hypocalcemia event according to the treatment intervention employed to manage the hypocalcemia. These will be considered separately by treatment and in combination (i.e. any treatment). Average percentage change in serum calcium from the value at the time of hypocalcemia occurrence will also be summarized.

Point estimates and 95% confidence intervals will be derived to determine the rate of CV events during the 12 months following cinacalcet initiation.

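### Table 1 bands PTH at <10, 10-65 and >65 pg/mL for the exploratory hypocalcemia-by-PTH outcome, which conflicts with Tables 2 and 3 and leaves little resolution in this population

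*Protocol*

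**What the plan says.** Protocol section 8.3 sets two exploratory objectives in Cohort B that depend on PTH grouping. Objective 8.3.2 reads "To explore the incidence of hypocalcemia events among HD patients with cinacalcet prescription according to PTH levels", and objective 8.3.3 reads "To explore the frequency of hypocalcemia events among HD patients with cinacalcet prescription according to PTH levels". Section 9.6.2.4 plans point estimates and 95% confidence intervals for the "rate of hypocalcemia according to PTH levels during the 12 months following cinacalcet initiation".

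The only PTH grouping attached to these outcomes is in Table 1 (section 9.3.2), in the row for incidence by PTH. Its lowest group lies below 10 pg/mL, and the other two are given as "normal (10-65 ng/L or pg/mL) or high (> 65 ng/mL or pg/mL". That row names incidence only. The frequency definition in 9.3.2.2 gives no PTH bands.

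Elsewhere the protocol groups PTH differently. Table 2 (section 9.3.3) uses "<150, 150-<300, 300-<600, ≥600" pg/mL. Table 3 (section 9.6.2.1) has the same cut-points, calling values below 150 low, then "Medium low 150<300", a medium-high band of 300 to below 600, and high from 600 upward.

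On the population, the abstract describes incident European HD patients with SHPT who were prescribed cinacalcet, and section 7.1 states: "Approximately 30-47% of severe CKD patients on dialysis in Europe are affected with SHPT (PTH>300 pg/mL").

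**The concern.** Cut-points of 10 and 65 pg/mL do not divide a population described as having SHPT on dialysis. If nearly everyone sits above 65, the stratified table gives one row that almost equals the overall result, beside two rows that are empty or very small. Patients far above, near and within the 150-300 pg/mL target range cited in section 7.1 would all share that one row, although any gradient of hypocalcemia risk with PTH would have to be read across those levels.

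There is also a labelling conflict. The same report would call one patient high under Table 1 and low under Table 3. The unit of the top band is inconsistent as well: ng/L and pg/mL are the same quantity, but ng/mL is 1000 times larger.

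**Working it through.** **1. The protocol's own figure.** No figure is given for the PTH strata. The only precision statement is in section 9.5: a maximum half width of 0.040 with 600 patients. Half width = 1.96 × √(p(1−p)/n). With p = 0.5 and n = 600 this is 0.0400, so it reproduces. The expected count is 1245 × 0.47 = 585, which the protocol rounds to about 600.

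**2. The bands side by side (no assumption needed).**

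| PTH (pg/mL) | Table 1 | Table 3 |
|---|---|---|
| <10 | low | low |
| 10-65 | normal | low |
| 66-149 | high | low |
| 150-<300 | high | medium low |
| 300-<600 | high | medium high |
| ≥600 | high | high |

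Three of the four Table 3 bands lie wholly inside the Table 1 top band, and the fourth straddles 65. Every patient who meets the SHPT level in 7.1 (above 300) is high in Table 1, and so is every patient inside the cited 150-300 target range.

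**3. Band occupancy (assumption).** Assume log-normal PTH at initiation with median m = 300 to 800 pg/mL and log-SD s = 0.5 to 0.9. Then P(PTH < x) = Φ[(ln x − ln m)/s].

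- Least favourable corner, m = 300 and s = 0.9: (ln 65 − ln 300)/0.9 = −1.529/0.9 = −1.70, so P(<65) = 0.045.
- Across the whole range, >65 holds 95.5-100%, 10-65 holds 0-4.5%, and <10 holds at most about 0.01%, which is about 0.1 of a patient among 1245.

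**4. What a small lower group could show.** Take 1245 patients (the section 9.5 count, an upper limit for Cohort B) and 47% with hypocalcemia. The share at or below 65 is an assumption. Half width = 1.96 × √(0.47 × 0.53/n). The last column is the smallest shortfall from 47% detectable with 80% power (two-sided 5%, normal approximation, pooled variance under the null).

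| Share ≤65 | n | Half width | Detectable difference |
|---|---|---|---|
| 0.5% | 6 | 0.39 | 45 points |
| 1% | 12 | 0.28 | 36 points |
| 2% | 25 | 0.20 | 27 points |
| 5% | 62 | 0.12 | 18 points |
| 10% | 125 | 0.09 | 13 points |

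The top band would have a half width of 0.028-0.029 throughout.

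**5. The same patients in the Table 2/3 bands.** With m = 450 and s = 0.7 the shares are 5.8%, 22.3%, 37.8% and 34.1%. Of 1245 patients that is about 73, 278, 471 and 424, with half widths at 47% of 0.115, 0.059, 0.045 and 0.047. All four rows could then be reported and compared.

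**The case against.** **Exploratory status.** The row serves exploratory objectives and no hypothesis is tested (section 7.3). The primary objectives, the study size in 9.5 and the primary and secondary analyses in 9.6.2.3 do not use these bands. This stands, and it limits the severity.

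**Partial cover elsewhere.** Objective 8.2.5 looks for factors associated with time to hypocalcemia in the same cohort, using Cox models on the Table 2 covariates. PTH is one of these, in the 150/300/600 bands. This stands in part: those models give hazard ratios for the first event, not incidence by stratum, and they do not cover event frequency.

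**No PTH entry rule.** Eligibility (9.2.2.1) sets no PTH threshold, and the 300 pg/mL in 7.1 belongs to a cited prevalence estimate. Table 1 does not say when PTH is measured, and on-treatment values could be lower. A reader might infer that the bands cannot show any difference by PTH. The protocol does not support that: if 5-10% of patients were at or below 65, differences of about 13-18 points could still be detected.

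**The unit.** A reader might infer that nobody qualifies as high, because 65 ng/mL is 65,000 pg/mL. That does not hold, because the cell also offers pg/mL, and the neighbouring bands show that ng/mL is a slip for ng/L.

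**Scope.** Use of the bands for 8.3.3 is an inference from the absence of any other grouping; Table 1 does not state it.

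**Conclusion.** The point holds as an internal contradiction and a poor choice of strata. The contradiction with Tables 2 and 3 rests on the printed cut-points alone. The near-collapse into one band rests on the protocol's description of its population and on the assumed log-normal range, which puts 95.5-100% of patients above 65; it is not a count. The consequence is little or no resolution across the PTH range these patients occupy, for 8.3.2 directly and for 8.3.3 by inference. Because the protocol itself fixes these bands, this is not a detail left to a statistical analysis plan. Severity is moderate: an exploratory tabulation is weakened, while the primary objectives and the Cox analysis for 8.2.5 are not affected.

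**What to change.** In Table 1, replace the three PTH bands with the Table 2/3 levels: <150, 150-<300, 300-<600 and ≥600 pg/mL. State that the grouping uses the most proximal PTH in the 90 days before cinacalcet initiation, in line with the Cohort B baseline in 9.2.3 and the covariate rule in 9.3.3. State that it applies to both 8.3.2 and 8.3.3. Correct ng/mL to ng/L wherever that unit is kept for PTH.

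The cost is one table cell and a sentence. No new data are needed, since section 9.4 says PTH is typically tested quarterly. Making the change before the analysis also avoids choosing cut-points after the results are seen.

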9.3.2.1 Incidence of hypocalcemia

The cumulative incidence of first hypocalcemia event (# of new cases with serum calcium value <8.4 mg/dL) will be calculated overall and stratified by mutually exclusive groups of mild (≥ 8.0 - < 8.4 mg/dL), moderate (≥ 7.5 - < 8.0 mg/dL), and severe (< 7.5 mg/dL).

The time period will be monthly following cinacalcet initiation. Patients are at risk for each specified time period if they have an active supply of cinacalcet and therefore at risk of hypocalcemia. Patients are not at-risk if they do not have an active supply of cinacalcet, died, had a parathyroidectomy or a renal transplant, or was lost to follow-up during the specified time period.

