Despite the potential effectiveness of cinacalcet to manage SHPT, tolerance of cinacalcet may be limited. RCTs show a 7-fold increased risk of hypocalcemia (RR=6.98; 95% CI: 5.10-9.53) (Ballinger *et al*, 2014; Sekercioglu *et al*, 2016). Similar to RCTs, hypocalcemia is commonly observed in patients treated with cinacalcet in observational studies (Kilpatrick *et al*, 2013; St Peter *et al*, 2009). Although cinacalcet is effective in reducing calcium and PTH, the rate of hypocalcemia events increased by five-fold from baseline (2.3% to 10.1%). In another study of over 7600 patients initiating cinacalcet from a large dialysis provider in the US, low calcium levels at baseline have been found to be predictive of cinacalcet discontinuation, however, hypocalcemia prior to discontinuation of cinacalcet did not appear to be a factor in the decision to reinstate use of cinacalcet (Kilpatrick *et al*, 2013). Its unclear how these hypocalcemia events may impact real-life cinacalcet utilization patterns and SHPT control.

In reponse to the development of cinacalcet-induced hypocalcemia (total calcium <8.4 mg/dl and >7.5 mg/dl), the Summary of Product Characteristics (SmPC) recommends clinicians to adjust calcium-containing phosphate binders, vitamin D sterols, dialysate calcium to raise serum calcium according their own clinical judgement (e.g. initiate, reduce or discontinue therapies); or if the patient has severe hypocalcemia (≤ 7.5 mg/dl), they are recommended to discontinue use until serum calcium levels are raised to levels of 8.0 mg/dl and symptoms have been resolved. Currently, there are limited data on the effectiveness of treatment interventions to manage cinacalcet-induced hypocalcemia and its impact on SHPT control. One observational study in the US found that 50% of patients who initiated cinacalcet experienced a hypocalcemia event (total calcium <8.4 mg/dL) (Brunelli *et al*, 2015). The proportion of patients who received at least one treatment intervention was directly related to increased severity of hypocalcemia: calcium <8.0-8.3 mg/dL (48.6%), 7.5-7.9 mg/dL (52.2%) and <7.5 (63.5%). The most common treatment intervention for low calcium was addition or up-titration of vitamin D

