7.2 Rationale

Hypocalcemia is a common adverse event in SHPT patients receiving cinacalcet as first-line treatment. Patients using cinacalcet are six times more likely to experience hypocalcemia (total calcium < 8.4 mg/dl) compared to those who do not use it (Sekercioglu *et al*, 2016). The adverse effect can be symptomatic (i.e. include paresthesias, numbness, tingling, myalgias or cramping) or asymptomatic (Bover *et al*, 2016). Any side effects such as hypocalcemia could adversely affect a patient's level of medication compliance and/or adherence or changes in treatment strategies (e.g. discontinuation of cinacalcet). The SmPC recommends adjustments of standard therapies (calcium-containing phosphate binders, vitamin D sterols, dialysate calcium) at the clinician's discretion and to discontinue use of cinacalcet when the hypocalcemia event is severe (total calcium < 7.5 mg/dl). Data from two clinical trials observed that $< 1\%$ of asymptomatic patients with hypocalcemia were withdrawn from cinacalcet treatment, suggesting that it is tolerable and manageable in most cases (Block *et al*, 2008; Schaefer *et al*, 2008). In contrast, discontinuation was observed to be much higher ($\sim 17\%$) in a US retrospective observational study (unpublished data from (Brunelli *et al*, 2015)). The discrepancy in cinacalcet discontinuation rates between clinical trials (Block *et al*, 2008; Schaefer *et al*, 2008) and the observational study (Brunelli *et al*, 2015) raises the question as to what factors will drive changes in treatment strategies in real-life clinical practice. Dose reduction or cinacalcet discontinuation may negatively affect SHPT control.

To date, treatment strategies to manage cinacalcet-induced hypocalcemia has not been well-characterized in a European HD population. In addition, it is unclear whether

patients who recover from hypocalcemia will achieve adequate SHPT control. Therefore, we propose to characterize clinician treatment and management practices in the AROii European HD population. Data are needed to inform appropriate treatment guidance on the management of hypocalcemia among SHPT patients using cinacalcet.

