9.2.4.1 Censoring

Patients will begin to accrue time at risk from the end of their relevant baseline period until they experienced hypocalcemia (*Cohort B*), discontinued cinacalcet (*Cohort 1*) or reinitiated cinacalcet (*Cohort C*). Patients will also be censored if they died, underwent parathyroidectomy or a renal transplant, or were lost to follow-up during the respective follow-up periods. Patients will be considered lost to follow-up if they left a dialysis facility for any reason and did not return to the same or another FMC facility within 45 days.

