9.6.2.6 Stratified Analysis

- All primary and secondary analysis will be reported overall for all hypocalcemia patients and stratified by severity: mild (serum calcium \geq 8.0 - $<$ 8.4 mg/dL), moderate (serum calcium \geq 7.5 - $<$ 8.0 mg/dL), severe (serum calcium $<$ 7.5 mg/dL).
- For objective 8.2.4, summary statistics of cinacalcet patients who develop and do not develop hypocalcemia shall be stratified by sex and age.

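### The severe-hypocalcemia incidence counts only patients whose first low calcium is already below 7.5 mg/dL, so patients who worsen after a milder first value are left out

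*Protocol*

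**What the plan says.** **Endpoint.** Section 9.3.2.1 defines the outcome as "The cumulative incidence of first hypocalcemia event (# of new cases with serum calcium value <8.4 mg/dL", and this "will be calculated overall and stratified by mutually exclusive groups of mild" (8.0 to below 8.4), moderate (7.5 to below 8.0) and severe (below 7.5 mg/dL).

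**Risk time.** Section 9.2.4.1: "Patients will begin to accrue time at risk from the end of their relevant baseline period until they experienced hypocalcemia" in Cohort B. Hypocalcemia here means any value below 8.4 mg/dL (9.3.1.2).

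**Table 1.** Under incidence of hypocalcemia, a second line reads "First occurrence of serum calcium defined by severity: mild", followed by the moderate and severe bands. The text directly after the table refers the reader to the more detailed definitions that follow, of which 9.3.2.1 is the first.

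**Stratification.** Section 9.6.2.6: "All primary and secondary analysis will be reported overall for all hypocalcemia patients and stratified by severity". It gives the bands but not the calcium value (first, latest or lowest) that places a patient in one.

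**Label background.** Section 7.1 says "if the patient has severe hypocalcemia (≤ 7.5 mg/dl), they are recommended to discontinue use". Section 7.2 says "discontinue use of cinacalcet when the hypocalcemia event is severe (total calcium < 7.5 mg/dl".

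**The concern.** A reader will take an incidence of severe hypocalcemia to mean the share of cinacalcet initiators who reach a severe value within 12 months. The plan as written estimates the share whose first low value is already severe. The two agree only if nobody worsens after a milder first value. The protocol itself treats that as open: section 9.3.2.7 asks whether hypocalcemia progresses slowly or whether patients drop straight into the severe range.

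This matters because sections 7.1 and 7.2 single out severe hypocalcemia as the level at which the label text addresses stopping the drug. An incidence that is low by construction could be quoted as reassurance. The severity gradient in treatment changes would also be hard to read beside the US gradient cited in 7.1 (48.6%, 52.2%, 63.5%) unless the report says which value defined severity.

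**Working it through.** **1. The plan's own figure.** Section 9.5 gives 1245 patients, 47% with hypocalcemia, Cohort 1 of about 600 and a maximum half width of 0.040. Check: 1245 × 0.47 = 585. Half width = 1.96 × √(0.25/n), which is 0.0400 at n = 600 and 0.0405 at n = 585. The figure reproduces. It concerns one proportion in all of Cohort 1 and says nothing about severity.

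**2. One patient through the text.** Calcium is 8.2 mg/dL in month 2 and 7.2 in month 3, on cinacalcet throughout.

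| Section | Treatment of this patient |
|---|---|
| 9.3.2.1 | First event is 8.2: mild, and in no other group |
| 9.2.4.1 | Risk time ends in month 2; 7.2 is outside it |
| Table 1, read as severity of the first event | Mild only |
| Table 1, read as first occurrence of each grade | Mild in month 2, severe in month 3 |

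The last reading conflicts with the first two rows.

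**3. Direction.** Let s be the share of Cohort 1 whose first low value is below 7.5 and e the share with any value below 7.5 within 12 months of initiation. Every patient in s is also in e, so e ≥ s. The under-count is e − s, which is zero only if nobody worsens. This needs no assumption about calcium.

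**4. Size, illustrative only.** The documents give neither s nor e. A simulation of 12 monthly values (section 9.4 says calcium is typically tested monthly) used eight assumed parameter sets of 200,000 patients each. Ranges were: patient mean 9.2–9.4 mg/dL (SD 0.4–0.6), mean fall on treatment 0.3–0.6, within-patient SD 0.3–0.6, autocorrelation 0–0.6, starting value at least 8.4. No treatment follows the first low value.

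| | 12-month incidence below 8.4 | s | e | Uncounted, (e − s)/e |
|---|---|---|---|---|
| Set with smallest loss | 65.8% | 6.2% | 23.5% | 73.4% |
| A middle set | 51.1% | 1.2% | 15.7% | 92.5% |
| Set with largest loss | 48.0% | 0.2% | 14.5% | 98.5% |

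The last column comes from unrounded values. Over all eight sets s is 0.2–6.2% and e is 14.1–25.0%. Per 600 patients that is about 1–37 counted as severe against 85–150 ever severe.

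**5. Allowing for treatment.** Let f be the share of ever-severe patients already severe at the first low value, and suppose treatment averts a fraction a of later severe cases. The uncounted share becomes (1 − f)(1 − a) / [(1 − f)(1 − a) + f].

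| | a = 0 | a = 0.5 | a = 0.9 |
|---|---|---|---|
| f = 0.266 | 73% | 58% | 22% |
| f = 0.015 | 98.5% | 97% | 87% |

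The sign is fixed; the size depends heavily on inputs that the documents do not give.

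**6. Discontinuation, if index severity sets the stratum.** Let w be the share of the mild stratum that later becomes severe, and q_s and q_m the stop rates with and without a later severe value. The share of stops in the mild stratum that follow a severe value is w·q_s / [w·q_s + (1 − w)·q_m]. With assumed w = 0.1–0.3, q_s = 0.30–0.63 and q_m = 0.10–0.17:
- lowest: 0.1 × 0.30 / (0.030 + 0.9 × 0.17) = 0.030/0.183 = 16%;
- highest: 0.3 × 0.63 / (0.189 + 0.7 × 0.10) = 0.189/0.259 = 73%.

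The simulation, again without treatment, put w at 0.11–0.20.

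**The case against.** **Table 1 may already ask for the right thing.** Its severity line can be read as first occurrence of each grade, and mutually exclusive may mean only that the bands do not overlap. This is fair, but the table defers to the detailed definitions, and the stop in risk time at any hypocalcemia rules that reading out. The text needs reconciling either way.

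**Worsening is observed elsewhere.** Section 9.6.2.1 summarizes time-varying covariates, total calcium among them, for the 90 days before discontinuation, and plots calcium after the hypocalcemia event. Section 9.6.2.4 plots calcium by treatment intervention, and 9.3.2.7 classifies progressors. All true, so later severe values are not invisible. None of these yields an incidence of severe hypocalcemia.

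**It is a secondary objective.** Incidence is objective 8.2.1 and no hypothesis is tested. The overall discontinuation rate in Cohort 1 and its precision do not depend on severity bands. This stands and limits the weight of the point.

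**Index severity is a sound stratifier.** It is fixed at time zero, so strata cannot depend on what happens later. This stands, and the fix keeps it.

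**A reader might infer that later stops are credited to mild hypocalcemia.** Section 9.6.2.6 does not say so. For Cohort 1, sections 9.2.3 and 9.6.2.3 lean towards the value at entry: the baseline period ends when hypocalcemia develops, and the Kaplan-Meier strata are set at baseline. For Cohort C, whose baseline runs up to discontinuation, the same rules lean towards a later value. The supportable statement is that the defining value is not named.

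**Conclusion.** The point holds for incidence. Under sections 9.3.2.1 and 9.2.4.1 together, severe incidence means that the first low value was already below 7.5 mg/dL. It under-counts patients who ever become severe unless nobody worsens, and Table 1 must be brought into line with those two sections.

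A reader might infer that severe hypocalcemia is largely missed. The documents do not support a size. The simulated 73 to 98.5% rests wholly on assumed calcium courses with no treatment after the first low value, while section 7.1 cites intervention in about half or more of US patients. Only the direction is certain.

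A reader might also infer that the study's severe band is inconsistent. It is not: Table 1, 9.3.2.1, 9.6.1.1 and 9.6.2.6 all place exactly 7.5 mg/dL in the moderate band. Only the two background accounts of the label, in 7.1 and 7.2, differ at exactly 7.5. They should be reconciled, but this is minor.

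**What to change.** 1. **Sections 9.3.2.1, 9.2.4.1 and Table 1.** Report the cumulative incidence of first value below 8.4, first value below 8.0 and first value below 7.5 mg/dL as three separate endpoints. For each, risk time continues past milder events; the other ends of risk time in 9.3.2.1 stay as they are. Reword the Table 1 line to match.
2. **Section 9.6.2.6.** State that severity at the index event is the fixed stratifier for Cohort 1. Add a description of discontinuation by time-updated calcium band (below 7.5, 7.5 to below 8.0, 8.0 to below 8.4, and 8.4 or above), as person-time rates or with a time-dependent covariate. The existing time-varying calcium covariate in Table 2 will not serve, because its lowest category is below 2.10 mmol/L, about 8.4 mg/dL. Do not stratify by the lowest value up to the treatment change: patients who stop have a short window and those who continue have up to 12 months, so strata would depend on length of observation.
3. **Sections 7.1 and 7.2.** Reconcile the two accounts of the label at exactly 7.5 mg/dL.

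Cost: wording, a few tables and one time-updated analysis, all from calcium data already held. The three incidence groups will overlap and will not sum to the total, which a table footnote should say.
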